9.4 Statistical Methods

The planned analyses will include descriptive statistics on the proportions of overall responses. The response probabilities will be estimated using the sample proportions and their inferences including confidence intervals and hypotheses testing will be evaluated using Binomial distributions, and, if appropriate, normal approximations. The time to responses, overall survival and the PFS time will be analyzed using appropriate nonparametric tools in survival analysis such as Kaplan-Meier estimates taking consideration of random censoring.

In addition, methods based on survival analysis, cumulative incidence rates and other competing risk models will be used to evaluate the treatment effects. Graphical tools will be used to display the appropriate estimates (i.e. estimated proportions and Kaplan-Meier curves) and their corresponding 95% confidence intervals. Methods based on multiple regression, analysis of variance, logistic regression and nonparametric regression will also be employed if deemed appropriate.

9.5 Study Stopping Rules

The study will be monitored to ensure that the occurrence of a specified set of treatment related serious adverse events (TRSAEs) that occur during the treatment period does not substantially exceed an anticipated rate. The following specified TRSAEs determined to be probably or definitely related to therapy will be considered for early stopping of the study

1. Death
2. Severe infection requiring vasopressor >24h or intubation
3. Any grade 4 toxicity **excluding**
 - readily reversible metabolic or laboratory abnormalities
 - hematologic toxicities

We anticipate the rate of these specified TRSAEs within the 6 months period (completion of primary endpoint) to be 15% or less. Following Geller et al. (2003, "Design of Early Trials in Stem Cell Transplantation: A Hybrid Frequentist-Bayesian Approach"),⁷⁹ our stopping rule is determined by a Bayesian approach. The stopping boundary for an experiment is reached if the Bayesian posterior probability that the true probability of developing one or more of the specified TRSAE's exceeds this benchmark rate of 15% is at least 90%. We take our prior distribution to be a beta distribution so that our prior clinical opinion is worth 20% of the weight we will place on the new data. This gives prior parameters $\alpha = 0.9$, $\beta = 5.1$. Hence when we make decisions about stopping the study, the data from the study will dominate over the prior opinion. We begin monitoring the TRSAEs when 3 subjects are evaluable for TRSAEs within the 6 months.

Number of subjects in the experiment	Stop if the number of subjects who have developed any of the specified TRSAE's reaches:
≤ 6	3
≤ 11	4
≤ 16	5
≤ 21	6
≤ 26	7
≤ 32	8

We investigated the performance of the above stopping rule by a simulation study. In each simulation run, we generated a study with 32 independent Bernoulli trials, each had a probability p for having TRSAE and $q=1-p$ for not having TRSAE and compared the TRSAE outcomes with the above stopping boundary to determine whether the study was stopped. We repeated the simulation 100,000 times and computed the proportion of stopped studies (i.e. “number of stopped studies”/100,000) which were stopped using the above stopping rule. The following table summarizes the proportions of stopped studies under a number of scenarios for p :

Probability of TRSAE = p	0.1	0.15	0.20	0.25	0.30
Proportion of Stopped Studies	4.4%	17.9%	41.3%	66.1%	84.2%
Average number of subjects	31.1	28.9	25.1	20.6	16.3
Average number TRSAEs	3.1	4.3	5.0	5.2	4.9

These results suggest that our stopping rule has a low probability stopping a study when the proportion of TRSAE is below the benchmark value of 15%, and the probability of stopping a study is high when the true proportion of TRSAE exceeds this benchmark value. Based on these results, we believe that our Bayesian stopping rule has satisfactory statistical properties.

9.6 Stopping rule for Mortality:

In addition, we have a stopping rule for TRM (death that are probably or definitely related to the protocol regimen and are not due to disease progression). We anticipate the TRM rate within one year to be 5% or less. Using the same Bayesian approach, the stopping boundary is reached if the Bayesian posterior probability that the true probability of developing TRM's exceeds 5% is at least 95%. We take our prior distribution to be a beta distribution with parameters $(\alpha, \beta) = (0.3, 5.7)$. This indicates that the relative weight we place on our prior opinion is approximately 20% of the weight we will place on the results of the new study. The following table summarizes the threshold numbers for stopping the study based on above Bayesian approach.

Number of subjects in the experiment	Stop if the number of subjects who have TRMs reaches:
≤ 9	2
≤ 21	3
≤ 32	4

We investigated the performance of the above stopping rule by a simulation study. In each simulation run, we generated a study with 32 independent Bernoulli trials, each had a probability p for having TRM and $q=1-p$ for not having TRM and compared the TRM outcomes with the above stopping boundary to determine whether the study was stopped. We repeated the simulation 100,000 times and computed the proportion of stopped studies (i.e. “number of stopped studies”/100,000) which were stopped using the above stopping rule. The following table summarizes the proportions of stopped studies under a number of scenarios for p :

Probability of TRM = p	0.03	0.05	0.07	0.10	0.15	0.20
Proportion of Stopped Studies	4.7%	14.2%	27.7%	49.6%	78.5%	93.0%
Average number of subjects	31.1	29.4	27.1	23.3	17.1	12.4
Average number TRMs	0.9	1.5	1.9	2.3	2.6	2.5

These results suggest that our stopping rule has a low probability stopping a study when the proportion of TRM is below the benchmark value of 5%, and the probability of stopping a study is high when the true proportion of TRM exceeds this benchmark value. Based on these results, we believe that our Bayesian stopping rule has satisfactory statistical properties.

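### Section 9.6 states a 95% posterior threshold for the treatment-related mortality stopping rule, but its boundary table and simulation results are those of a 90% threshold

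*Combined protocol and SAP*

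**What the plan says.** Section 9.6 sets the benchmark: "We anticipate the TRM rate within one year to be 5% or less". The boundary is reached when the posterior probability that the true TRM rate "exceeds 5% is at least 95" percent. The prior is Beta(0.3, 5.7), and its weight is described so: "the relative weight we place on our prior opinion is approximately 20% of the weight we will place on the results of the new study".

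Next comes the boundary: "The following table summarizes the threshold numbers for stopping the study based on above Bayesian approach". The table's instruction is "Stop if the number of subjects who have TRMs reaches" 2 (up to 9 subjects), 3 (up to 21) or 4 (up to 32).

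For the operating characteristics, "we generated a study with 32 independent Bernoulli trials, each had a probability p for having TRM", and each simulated study was compared with that boundary, 100,000 times. The reported "proportion of stopped studies" is 4.7, 14.2, 27.7, 49.6, 78.5 and 93.0% at true TRM of 3, 5, 7, 10, 15 and 20%. The section concludes that the rule's properties are satisfactory.

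Section 9.5 has a companion rule for treatment-related serious adverse events (TRSAEs), with prior Beta(0.9, 5.1). It stops when the posterior probability that the rate "exceeds this benchmark rate of 15% is at least 90" percent. Section 9.6 says that it uses the same Bayesian approach.

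**The concern.** The table is presented as the numerical form of the sentence above it, so the two must give the same decision at every sample size. The prior, benchmark, threshold and maximum sample size are all printed, so this can be checked without outside assumptions.

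If they differ, the study has two mortality stopping rules. Section 10.0 asks for DSMB review because ibrutinib and fludarabine are being combined in a clinical trial for the first time. A board that reads the table and a board that computes the posterior from the sentence could reach opposite decisions on the same deaths. The finding that the rule performs satisfactorily would also rest on a simulation of a rule other than the one the text defines.

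**Working it through.** **Inputs (Section 9.6).** Prior Beta(0.3, 5.7): mean 0.3/6 = 5%, worth 6 subjects, and 6/32 = 18.75%, consistent with the stated weight of about 20%. Benchmark 5%. Stated threshold 0.95. Maximum 32 subjects.

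**Formula.** After x treatment-related deaths in n subjects, the posterior is Beta(0.3 + x, 5.7 + n − x). The boundary at n is the smallest x for which P(p > 0.05) under that posterior reaches the threshold.

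**Check of the method on Section 9.5.** With Beta(0.9, 5.1), a 15% benchmark and a threshold of 0.90, the calculation reproduces the TRSAE boundary exactly from the third subject, where monitoring begins: 3 to n = 6, 4 to 11, 5 to 16, 6 to 21, 7 to 26, 8 to 32. The exact stopping probabilities of that boundary are 4.5/18.1/41.2/65.9/84.2%, against 4.4/17.9/41.3/66.1/84.2% printed. The method is therefore the plan's own.

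**The printed TRM boundary.** Posterior probability at the end of each row, and one subject later:

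| Deaths | Last n in printed row | Posterior | P(p > 5%) | At n + 1 |
|---|---|---|---|---|
| 2 | 9 | Beta(2.3, 12.7) | 0.902 | 0.888 |
| 3 | 21 | Beta(3.3, 23.7) | 0.903 | 0.893 |
| 4 | 32 | Beta(4.3, 33.7) | 0.919 | study maximum |

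No row end reaches 0.95. Each is at least 0.90, and the two internal row breaks fall exactly where the probability drops below 0.90. A 0.90 threshold reproduces the whole printed table.

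**The boundary that the sentence implies (0.95).**

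| Deaths | Last n | P(p > 5%) | At n + 1 |
|---|---|---|---|
| 2 | 5 | 0.951 | 0.940 |
| 3 | 15 | 0.951 | 0.944 |
| 4 | 26 | 0.954 | 0.949 |
| 5 | 32 | at least 0.95 | study maximum |

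Seven other priors with mean 5% and total weight from 4 to 32 subjects were also tried. None gives the printed table at 0.95.

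**Where the two disagree.** At 2 deaths with n = 6–9 (4 sample sizes), 3 deaths with n = 16–21 (6) and 4 deaths with n = 27–32 (6): 4 + 6 + 6 = 16 of the 32 possible sample sizes. In each, the table stops and the sentence continues.

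**Operating characteristics.** These come from exact recursion over 32 Bernoulli subjects, checked after each one. Starting the checks at subject 1, 2 or 3 leaves the stopping probabilities unchanged.

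| True TRM | 3% | 5% | 7% | 10% | 15% | 20% |
|---|---|---|---|---|---|---|
| Stopped, as printed (%) | 4.7 | 14.2 | 27.7 | 49.6 | 78.5 | 93.0 |
| Stopped, printed boundary, recomputed (%) | 4.7 | 14.2 | 27.5 | 49.6 | 78.6 | 93.0 |
| Stopped, stated 95% rule (%) | 2.0 | 7.1 | 16.0 | 34.2 | 65.5 | 86.1 |
| Mean subjects, as printed | 31.1 | 29.4 | 27.1 | 23.3 | 17.1 | 12.4 |
| Mean subjects, printed boundary, recomputed | 31.1 | 29.4 | 27.2 | 23.3 | 17.1 | 12.4 |
| Mean subjects, stated 95% rule | 31.6 | 30.7 | 29.2 | 26.1 | 20.3 | 15.1 |

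The largest gap between printed and recomputed stopping proportions is 0.2 percentage points, at 7%. The simulation standard error there is √(0.275 × 0.725 / 100,000) = 0.14 points, so the gap is about 1.4 standard errors. The 95% rule differs from the printed proportions by 2.7 to 15.4 points, which simulation error cannot explain. The printed mean numbers of TRMs (0.9/1.5/1.9/2.3/2.6/2.5) also match the recomputed printed boundary.

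**The case against.** The strongest reply is that this is one wrong number in one sentence. The count table is what a board would use in practice. The simulation was run on that table, its results are correct for it, and Section 9.6 says it follows the approach of Section 9.5, where the threshold is 90%. The table is also the more cautious version: it stops earlier at every point of disagreement, and at a true TRM of 5% it stops 14.2% of studies against 7.1%. Anyone following the table protects subjects at least as well as the sentence would. The DSMB also reviews safety every six or twelve months and may recommend stopping.

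Most of this stands. The table, simulation and conclusion agree with one another, and following the table is the protective reading. But nothing in Section 9.6 gives the table precedence: the sentence defines the boundary and the table is said to summarise it. A slip in the sentence is plausible, but the documents do not show which side is in error. The TRSAE rule does not settle the matter either. It counts treatment-related deaths, but against a 15% benchmark over six months, and it needs at least 3 events. Periodic review does not tell the board which of the two rules it is to apply.

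**Conclusion.** The concern holds. Under the printed prior and benchmark, the boundary and all the operating characteristics in Section 9.6 belong to a 90% threshold, while the text states 95%. The two give opposite decisions at 16 of 32 sample sizes when the death count sits on the printed boundary. At a true TRM of 10%, the rule as worded would stop 34.2% of studies, 15.4 points fewer than the 49.6% reported. The result uses only inputs printed in the plan and assumes, as the plan's simulation does, independent subjects with a common TRM probability; the recursion checks the boundary after each one. This needs correcting before the rule is relied on, because a mortality stopping rule must give one answer.

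**What to change.** Decide which threshold is intended and make Section 9.6 consistent. There are two ways:

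- **Change the sentence to 90%.** The boundary then stands as printed, and the operating characteristics stand within simulation error. The cost is one number.
- **Keep 95%.** Replace the boundary with 2 (up to 5 subjects), 3 (up to 15), 4 (up to 26) and 5 (up to 32). Replace all three rows of the operating-characteristics table, for true TRM of 3/5/7/10/15/20%: stopped 2.0/7.1/16.0/34.2/65.5/86.1%; mean subjects 31.6/30.7/29.2/26.1/20.3/15.1; mean TRMs 0.9/1.5/2.0/2.6/3.0/3.0. The concluding statement on the rule's properties should then be reconsidered against these lower stopping probabilities. The cost is two small tables.

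Either way, the text should say that the count table is the operative rule and the DSMB should be told of the correction. Enrolment and study procedures do not change.

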9.7 Off Study Criteria (for subject participation)

Patient choice: Subjects may be removed from the study at their request. The risks of withdrawing will be discussed, as will alternative treatment options. Subjects who opt to withdraw from the protocol will be strongly encouraged to continue to have labs (CBC, chemistries) monitored for two months after study withdrawal for their safety.

PI Decision: Study drug administration will be discontinued for adverse events as detailed in section 5.5. These subjects will be followed until resolution of the event and continue to be followed on protocol. Other off study criteria include:

- Initiation of non-protocol treatment.
 - For patients who were newly diagnosed with a second malignancy, the study drug can be interrupted while the patient undergoes further evaluation and treatment with definitive, time-limited systemic therapy (i.e. breast cancer requiring surgery and adjuvant chemoradiation). If the new second malignancy requires long-term therapy (>6 months) or a definite therapy is not available (i.e. metastatic solid tumor), the patient will be taken off study.
- Significant progression of disease or a concomitant condition that would make the subject ineligible for further protocol participation. In selected cases, PI can decide if ibrutinib may be continued after progression until contingency plan for the next line of therapy is in place, and the benefit of treatment continuation outweighs potential risks.
- Pregnancy or begins breast feeding
- Subject becomes significantly noncompliant with study drug administration, study procedures, or study requirements, which might increase risk or substantially compromise the interpretation of study results.

Completion of the study: Subjects will be followed indefinitely until an off study criterion is met or the study is closed to further follow up care.

Once protocol participation is complete, the subject will be referred back to his or her referring physician, consented to the Hematology Branch evaluation and treatment protocol (94-H-0010) for consideration for standard therapy or evaluated for eligibility for another branch protocol, depending on what is considered to be in the best interest of the subject.

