9.0 BIOSTATISTICAL CONSIDERATIONS

9.1 Primary endpoint:

Primary efficacy endpoint is the rate of complete response at 24 weeks or after 6 cycles. Response to treatment will be determined according to IWCLL 2008 criteria incorporating 2012 and 2013 clarifications pertaining to patients treated with kinase inhibitors.

Primary safety endpoint is the rate of treatment discontinuation within the first 24 weeks or 6 cycles due to intolerable side effects.

9.2 Secondary endpoints:

- Progression-free survival (PFS)
- Overall survival (OS)
- Best response during treatment
- Duration of response
- Minimal residual disease (MRD) state defined by flow cytometry
- Clonal dynamics on treatment assessed using interphase FISH and gene sequencing for somatic mutations
- Shifts in cellular and humoral immunity on treatment (e.g. immunoglobulin levels, myeloid-derived stromal cells, B-cell repertoire, T-cell subsets including regulatory T cells, T helper 1, T helper 2, T helper 17)
- Expression of checkpoint inhibitory molecules such as PD-L1, PD-1, and CTLA-4

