10.4.1 Reporting Period for AEs

The AE reporting period for this study begins when the patient takes the first dose of study drug and ends with the safety follow-up visit. If an SAE is present at the safety follow-up visit or within 30 days of the last dose of study drug (whichever is later), it should be followed to resolution or until the Investigator assesses the subject as stable, a new anticancer therapy is initiated, or the subject is lost to follow-up or

withdraws consent. Resolution/stable means the subject has returned to baseline state of health or the Investigator does not expect any further improvement or worsening of the event.

Reporting for other malignancies

Occurrences of any new malignant tumors including solid tumors, skin malignancies and hematologic malignancies will be reported throughout study participation, including duration of study treatment and during any protocol specified follow-up periods including post-progression follow-up for overall survival.

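### Sections 5.5.3, 9.7 and 10.4.1 conflict on follow-up after progression, and 9.7 ends it at new therapy; if 9.7 is followed, Kaplan-Meier overall survival is informatively censored

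*Combined protocol and SAP*

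**What the plan says.** OS is listed among the secondary endpoints in Section 9.2, without a definition, time origin or censoring rule. Section 9.4 gives the method: "The time to responses, overall survival and the PFS time will be analyzed using appropriate nonparametric tools in survival analysis such as Kaplan-Meier estimates". On censoring, that section says only that this is done "taking consideration of random censoring".

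Section 9.7 sets the end of follow-up: "Subjects will be followed indefinitely until an off study criterion is met or the study is closed to further follow up care". The off-study criteria include "Initiation of non-protocol treatment" (with an exception for time-limited treatment of a second malignancy) and "Significant progression of disease or a concomitant condition that would make the subject ineligible for further protocol participation". In selected cases the investigator may continue ibrutinib after progression. The section then states: "Once protocol participation is complete, the subject will be referred back to his or her referring physician", or the subject moves to another branch protocol. It describes no later contact for vital status.

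Two sections point the other way. Section 10.4.1, in its rule on reporting new malignancies, counts among the follow-up periods of the protocol one described as "including post-progression follow-up for overall survival". Section 5.5.3 puts progressive disease on its list of reasons for permanent discontinuation of study drug, and says that patients who can receive no more drug stay in regular follow-up with disease reassessment under Sections 6 and 7.

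Section 6 closes with the evaluation at progression (6.4), which is also the last column of Appendix A.

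**The concern.** Kaplan-Meier estimates survival correctly only if subjects censored at a given time have the same later risk of death as those still observed. Progression and the start of another CLL therapy are likely markers of higher risk. If observation stops there, later deaths may drop out of the OS analysis, and the curve drifts towards one for death before progression.

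Section 9.4 assumes random censoring but does not say how OS is handled for subjects who go off study. What is at stake is the OS curve and any informal comparison with published ibrutinib or chemoimmunotherapy series. Vital status that was not collected may also be hard to recover years later.

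**Working it through.** **1. The sections side by side**

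| Event | 5.5.3 | 9.7 | 10.4.1 | Section 6 / Appendix A |
|---|---|---|---|---|
| Drug stopped for an adverse event | follow-up continues | follow-up continues | – | – |
| Progression | on the list after which follow-up continues | off study if significant; follow-up ends | assumes survival follow-up afterwards | progression visit is the last item |
| New non-protocol therapy | not addressed | off study; follow-up ends | not addressed | nothing scheduled |

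No order of precedence is stated. Progression is contradictory; new therapy is an uncontradicted exit.

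**2. Size of the bias if 9.7 is followed**

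The plan states no OS figure, event count or power, so there is nothing of its own to reproduce. I used an illness-death model with constant hazards per year: a for progression, b for death without progression, c for death after progression.

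- True OS(t) = exp(−(a+b)t) + a[exp(−ct) − exp(−(a+b)t)] / (a+b−c)
- Kaplan-Meier with everyone censored at progression tends to exp(−bt)

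Input from the documents: 30-month PFS of 96% with frontline single-agent ibrutinib (Section 2.6.2). Hence a+b = −ln(0.96)/2.5 = 0.0163 per year, and 5-year PFS is 0.96² = 0.9216.

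Inputs assumed, because the documents do not give them: how a+b divides between progression and death, and the value of c.

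*Low end.* b = 0.01, so a = 0.0063; c = 0.10.
- Censored Kaplan-Meier at 5 years: exp(−0.05) = 0.951
- True OS: 0.9216 + 0.0063 × (exp(−0.5) − 0.9216)/(0.0163 − 0.10) = 0.9216 + 0.0238 = 0.945
- Overstatement: 0.6 points. With c = 0.30 it is 1.4 points.

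*High end.* A quarter of PFS events are deaths, so b = 0.0041 and a = 0.0122; median survival after progression is 12 months, so c = 0.693.
- Censored Kaplan-Meier at 5 years: exp(−0.0041 × 5) = 0.980
- True OS: 0.9216 + 0.0161 = 0.938
- Overstatement: 4.2 points

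Other combinations, with overstatement in points:

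| Deaths as share of PFS events | Median survival after progression | 30 months | 60 months | 84 months |
|---|---|---|---|---|
| 25% | 12 months | 1.6 | 4.2 | 6.4 |
| 25% | 24 months | 1.0 | 3.1 | 5.0 |
| 25% | 48 months | 0.6 | 1.9 | 3.3 |
| 50% | 12 months | 1.0 | 2.8 | 4.2 |
| 50% | 24 months | 0.6 | 2.0 | 3.3 |
| 50% | 48 months | 0.4 | 1.2 | 2.2 |
| either | no rise (c = b) | 0 | 0 | 0 |

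*More frequent progression.* With the relapsed-disease PFS in Section 2.6.2 (75% at 26 months), and the same splits and medians, the overstatement is 1.6 to 10.7 points at 30 months and 4.8 to 24.6 at 60 months. That is a different population and serves only as a pessimistic bound.

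**3. Scale in subjects**

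At 96% PFS, 27 × 0.04 = 1.1 subjects (32 × 0.04 = 1.3) would have progressed or died by 30 months. At 5 years the model gives 27 × (1 − 0.9216) = 2.1. The 95% half-width for 95% survival in 27 subjects is about 1.96 × √(0.95 × 0.05/27) = 0.082, or 8 points (simple binomial, no censoring).

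**The case against.** A reader might infer that OS will be censored at progression and is therefore certain to be overstated. The documents do not support that. No section says OS is censored at off study; 10.4.1 presupposes survival follow-up after progression; and 5.5.3 keeps patients who stop drug for progressive disease in follow-up. Section 9.7 removes subjects only for significant progression and allows ibrutinib to continue in selected cases.

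Nor is it established that deaths after progression go uncaptured. Section 10.3.3 requires deaths to be reported once the investigator learns of them. Some subjects move to another branch protocol, Section 6.0 allows results from other NIH protocols to be used, and Section 10.5 allows abstraction from home physicians' notes.

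A reader might also assume progression of 4–8% a year with 1% a year death before progression, and arrive at an overstatement of 3 to 16 points at 5 years. That arithmetic is correct (true OS 0.917 to 0.796 against 0.951), but those rates imply 30-month PFS of 88% and 80%, well below the cited frontline 96%.

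Finally, OS is descriptive: it has no hypothesis, comparator or power, and is absent from the secondary objectives in Section 1.2. The bias at 5 years is smaller than the sampling error.

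Most of this stands, and it limits the point to a contradiction with a conditional bias. It does not remove the point. The mention in 10.4.1 relies on a follow-up period that no section sets up. The cross-reference in 5.5.3 leads to three-monthly visits in 6.2 that run only on therapy and until progression; the annual assessments in 6.3 carry no such limit, but nothing says they continue after progression. The routes to learning of deaths are passive. None of these texts addresses new therapy. A bias is also not averaged away as sampling error is, and follow-up is meant to be open-ended, so the later time points matter.

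**Conclusion.** The point holds as an unresolved contradiction between 5.5.3, 9.7 and 10.4.1 on progression, together with an uncontradicted end of follow-up at new therapy and no OS censoring rule.

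If 9.7 is followed, Kaplan-Meier OS is informatively censored, and biased upward when the death hazard rises after progression. Anchored to the cited frontline PFS, the overstatement is about 0.6 to 4 points at 5 years. This rests on constant hazards, on assumed event splits and post-progression hazards, on single-agent PFS carrying over to the combination, and on every subject being censored at progression. If subjects instead stay until new therapy starts, the size depends on the time to that therapy and survival after it, which the documents do not give.

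The complete-response and discontinuation endpoints at six cycles are unaffected. This is a worthwhile amendment to a descriptive secondary endpoint and no threat to the main conclusions.

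**What to change.** 1. Reconcile 5.5.3, 9.7 and 10.4.1 by separating two statuses: off treatment or study visits, and off survival follow-up. Meeting an off-study criterion would end the first only.
2. Add to 9.7 and Appendix A a check of vital status and date of next therapy every 6 to 12 months, by phone or records and subject to consent, until death, withdrawal of consent or study closure.
3. Define OS in Section 9, including its time origin, and state in 9.4 that it is censored only at the date last known alive. Progression, new therapy and going off study would not be censoring events.

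The cost is a short amendment and a small periodic contact burden for about 27 to 32 subjects. No visit, procedure or treatment rule changes. Withdrawal of consent would still cause some loss, which should be reported as a count alongside the OS curve.
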